11.2. Procedures for Reporting Adverse Events and Serious Adverse Events

All AEs (serious and non-serious) spontaneously reported by the subject and/or in response to an open question from study personnel or revealed by observation, physical examination, or other diagnostic procedures will be recorded on the appropriate page of the eCRF. Any clinically relevant deterioration in laboratory assessments or other clinical findings is considered an AE and must be recorded on the appropriate pages of the eCRF. When possible, signs and symptoms indicating a common underlying pathology should be noted as one comprehensive event (ie, a diagnosis).

For reports of SAEs, Investigators should record all case details that can be gathered promptly on the AE eCRF and submit via the Electronic Data Capture (EDC) system. All SAEs are to be reported within 24 hours from the point in time when the Investigator becomes aware of the

SAE. All SAEs must be reported whether or not they are considered causally related to AG-120/placebo. Serious adverse event forms will be completed, and the information collected will include subject number, a narrative description of the event, and an assessment by the Investigator as to the severity of the event and relatedness to study drug. Follow-up information on the SAE may be requested by the Sponsor or Medical Monitor.

In the event that the EDC system is unavailable, a paper SAE and fax coversheet should be completed and faxed/emailed within no more than 24 hours after learning of the event using the fax numbers provided to Investigators per the safety reporting instructions.

If there are serious, unexpected related AEs associated with the use of AG-120/placebo, the Sponsor will notify the appropriate regulatory agency(ies) and all participating Investigators on an expedited basis. The local Institutional Review Board (IRB)/Independent Ethics Committee (IEC) will be promptly notified based on local regulations where required by the IRB/IEC of all serious, unexpected related AEs involving risk to human subjects.

All AEs, whether serious or not, will be described in the source documents and on the AE page of the eCRF. All new events, as well as those that worsen in severity or frequency relative to baseline, which occur after subjects have received at least one dose of study treatment through 28 days following the last dose of study treatment, must be recorded. Adverse events that are ongoing at the time of treatment discontinuation should be followed through the 28-day post-treatment assessment. In addition, SAEs that are assessed by the Investigator as related to study drug must be reported any time the Investigator becomes aware of such an event, even if this occurrence is more than 28 days after the last dose of study treatment.

Information to be reported in the description of each AE includes:

- A medical diagnosis of the event (if a medical diagnosis cannot be determined, a description of each sign or symptom characterizing the event should be recorded)
- The date of onset of the event
- The date of resolution of the event
- Whether the event is serious or not
- Severity of the event (see below for definitions)
- Relationship of the event to study treatment (see below for definitions)
- Action taken: none; change in the study treatment administration (eg, temporary interruption in dosing); drug treatment required; non-drug treatment required; hospitalization or prolongation of hospitalization required (complete SAE page); diagnostic procedure performed; subject discontinued from the study (complete End of Study Visit)
- Outcome: subject recovered without sequelae; subject recovered with sequelae; event ongoing; subject died (notify the Medical Monitor within 24 hours, and complete the SAE form)

Severity of all AEs, including clinically significant treatment-emergent laboratory abnormalities, will be graded according to the NCI CTCAE version 4.03 (Appendix 15.8). Adverse events not listed by the NCI CTCAE will be graded as follows:

- Mild: the event is noticeable to the subject but does not interfere with routine activity.
- Moderate: the event interferes with routine activity but responds to symptomatic therapy or rest.
- Severe: the event significantly limits the subject's ability to perform routine activities despite symptomatic therapy.
- Life-threatening: an event in which the subject was at risk of death at the time of the event.
- Fatal: an event that results in the death of the subject.

11.2.1. Diagnosis versus Signs and Symptoms

A diagnosis (if known) should be recorded on the Adverse Event eCRF rather than individual signs and symptoms (eg, record only liver failure or hepatitis rather than jaundice, asterixis, and elevated transaminases). However, if a constellation of signs and/or symptoms cannot be medically characterized as a single diagnosis or syndrome at the time of reporting, each individual event should be recorded on the Adverse Event eCRF. If a diagnosis is subsequently established, all previously reported adverse events based on signs and symptoms should be nullified and replaced by 1 AE report based on the single diagnosis, with a starting date that corresponds to the starting date of the first symptom of the eventual diagnosis.

11.2.2. Adverse Events Occurring Secondary to Other Events

In general, AEs occurring secondary to other events (eg, cascade events or clinical sequelae) should be identified by their primary cause, with the exception of severe or serious secondary events. However, medically significant AEs occurring secondary to an initiating event that are separated in time should be recorded as independent events on the Adverse Event eCRF. For example:

- a. If vomiting results in mild dehydration with no additional treatment in a healthy adult, only vomiting should be reported on the eCRF.
- b. If vomiting results in severe dehydration and requires treatment, both events should be reported separately on the eCRF.
- c. If a severe gastrointestinal hemorrhage leads to renal failure, both events should be reported separately on the eCRF.
- d. If dizziness leads to a fall and subsequent fracture, all 3 events should be reported separately on the eCRF.
- e. If neutropenia is accompanied by a mild, non-serious infection, only neutropenia should be reported on the eCRF.
- f. If neutropenia is accompanied by a severe or serious infection, both events should be reported separately on the eCRF.

All AEs should be recorded separately on the Adverse Event eCRF if it is unclear as to whether the events are associated.

11.2.3. Adverse Events of Special Interest

An AESI can be serious or nonserious and is an event of special interest to the Sponsor. Ongoing monitoring and rapid communication (within 24 hours) by the Investigator to the Sponsor is required to allow for further characterization and reporting to regulatory authorities.

11.2.3.1. QTcF Prolongation

Any QT prolongation event assessed as Grade 2 or worse (e.g., QTcF interval longer than 480 msec or 60 msec or longer than the reading at baseline with Torsade de pointes or polymorphic ventricular tachycardia or signs/symptoms of serious arrhythmia), irrespective of the seriousness of the event, should be reported as an AESI to the Sponsor within 24 hours. See Section 9.9 for further details on managing subjects with QTcF Prolongation. See Appendix 15.4 for Fridericia's formula.

11.2.4. Persistent or Recurrent Adverse Events

A persistent AE is one that extends continuously, without resolution, between subject evaluation time points. The initial severity of the event should be recorded, and the severity should be updated to reflect the most extreme severity any time the event worsens in intensity or grade.

When an AE becomes serious (regardless of changes in grade or severity), the eCRF should be updated to reflect this. As such, a new AE (serious event with onset date for when AE became serious) should be added to the eCRF.

However, the same does not hold true for AEs that change from serious to non-serious events. When an AE does not resolve but is downgraded from a serious to a non-serious event, a new AE is not required to be captured on the eCRF. A resolution date is required to be entered on the SAE form once an AE changes from a serious to non-serious event since this would result in the SAE resolving.

A recurrent AE is one that resolves between subject evaluation time points and subsequently recurs. Each recurrence of an AE should be recorded separately on the Adverse Event eCRF.

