9. SAFETY ANALYSIS

Unless specified otherwise, the safety data will be summarized by treatment based on SAS. Specifically, it will include placebo before crossover, AG-120 as dosed, AG-120 after crossover, and total AG-120. The total AG-120 includes all the subjects who have ever been dosed with AG-120 (that is, the sum of AG-120 as dosed and AG-120 after crossover). If a subject receives at least one dose of AG-120, the actual arm will be AG-120 as dosed. The same rule applies to the after crossover.

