9.1. Adverse Events

Treatment emergent adverse events (TEAEs) are defined as any AEs that begin or worsen on or after the start of study drug through 28 days after the last dose of study drug. All AEs will be coded using the Medical Dictionary for Regulatory Activities (MedDRA) dictionary, unless otherwise specified. The severity will be graded based on the NCI CTCAE. All AEs will be listed. Only TEAEs will be summarized and will be referred to as AEs hereafter.

If a subject experiences multiple AEs under the same PT within an SOC, then the subject will be counted only once for that PT within that SOC. If a subject experiences the same AE more than once with different intensity or grade, then the event with the highest grade will be tabulated in “by grade” tables.

Tables summarizing the incidence of AEs will be generated by treatment arms for each of the following:

- Overall summary of AEs
- All AEs by SOC and PT
- Most common AEs by PT (ie, those events reported by $\geq 5\%$ of subjects in any treatment group)
- Most common Treatment-Related AEs by PT (ie, those events reported by $\geq 5\%$ of subjects in any treatment group)
- Grade 3 or higher AEs by SOC and PT
- Most common Grade 3 or higher AEs by PT (ie, those Grade 3 or higher AEs reported by $\geq 5\%$ of subjects in any treatment group)
- Related AEs by SOC and PT
- Related Grade 3 or higher AEs by SOC and PT.
- SAEs by SOC and PT
- Related SAEs by SOC and PT
- AEs leading to study drug discontinuation by SOC and PT
- AEs leading to study drug reduced by SOC and PT
- AEs leading to study drug held by SOC and PT
- Related AEs leading to study drug discontinuation by SOC and PT

- Related AEs leading to study drug reduced by SOC and PT
- Related AEs leading to study drug held by SOC and PT
- On-treatment death due to AE by SOC and PT, where on-treatment is defined as within 28 days of last dose.
- On-treatment death due to related AE by SOC and PT, where on-treatment is defined as within 28 days of last dose.

All AEs will be listed by subject. By-subject listings will be provided for AEs leading to on-treatment death, SAEs, and AEs leading to discontinuation of treatment.

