9.2. Adverse Events of Special Interest

QT prolongation AEs will be summarized for the following:

- a) QT prolongation all grades by PT
- b) QT prolongation Grade 3 or higher by PT
- c) Treatment-related QT prolongation all grades by PT

Time to first QT prolongation AE will be summarized continuously and by ≤ 15 days, 16-30, 31-45, 46-60, and >60 days for all grade and Grade 2 or higher AEs.

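### A continuing adverse event takes on its worst grade with no date of worsening, so AG-120 toxicity can be shown under placebo and Grade 2 or higher QT prolongation can be timed too early

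*Protocol*

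**What the plan says.** **Collection.** Protocol 11.2.4 defines a persistent AE as one that runs on between evaluations without resolving. Its initial severity is recorded and then "the severity should be updated to reflect the most extreme severity any time the event worsens in intensity or grade". Two situations lead to a further record. When an AE becomes serious, "a new AE (serious event with onset date for when AE became serious) should be added to the eCRF". When an AE resolves and comes back, "Each recurrence of an AE should be recorded separately on the Adverse Event eCRF". A rise in grade without seriousness is in neither group. The items that Protocol 11.2 lists for each AE include "The date of onset of the event", the resolution date and the severity. A date of grade change is not among them.

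**Analysis.** SAP 9.1 states: "Treatment emergent adverse events (TEAEs) are defined as any AEs that begin or worsen on or after the start of study drug", with a window that closes 28 days after the last dose. When the same AE occurs more than once at different grades, the by-grade tables take the highest. For the safety summaries, SAP 9 says that "it will include placebo before crossover, AG-120 as dosed, AG-120 after crossover, and total AG-120". SAP 9.2 summarises time to first QT prolongation, continuously and in day bands, "for all grade and Grade 2 or higher AEs".

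**The concern.** Two planned outputs depend on when a grade was reached, and the stated recording rule does not ask for that date.

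The first is the split at crossover. A subject may begin a Grade 1 AE on placebo, cross over with it ongoing, and reach Grade 3 on AG-120 without the event becoming serious. The record then holds one onset date, on placebo, and one current severity, Grade 3. The event qualifies as a placebo event because it began there, and the grade available for the placebo by-grade table is one that was reached on AG-120. An error of this kind can only raise the placebo grade, so it makes AG-120 look better in the safety comparison.

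The second is the timing of QT prolongation, the only AE of special interest that the protocol names. If a Grade 1 record is later updated to Grade 2, a Grade 2+ analysis based on the AE onset date counts it from the day on which it was still Grade 1.

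**Working it through.** The plan gives no figure of its own on this point. The check sets the recording rule beside the outputs that use it, then does simple arithmetic on the planned sample size and the nominal ECG schedule.

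**1. Which grade increases carry a date (Protocol 11.2 and 11.2.4)**
- The AE resolves and returns: separate record, so dated.
- The AE becomes serious: new record with its own onset date, so dated.
- The AE continues, worsens and stays non-serious: severity updated on the existing record, and no date of worsening requested.

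Section 11.2.4 does not say in words that the first onset date is kept. That is an inference from its asking for a new onset date only in the serious case.

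**2. What the SAP needs for the third group**
- Placebo column: the highest grade reached before the first AG-120 dose.
- After-crossover column: whether the AE worsened against the crossover baseline, which SAP 10.3 resets to the last assessment before AG-120. This needs the grade at crossover and the date of the increase.
- SAP 9.2: the date on which Grade 2 was first reached.

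SAP 7.5 gives a crossover allocation rule based on start date for concomitant medications and procedures. No matching rule is written for AEs. The AE date rules in SAP 10.5 deal only with start and stop dates.

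**3. Size at crossover**
- Planned placebo arm: about 62 subjects (Protocol 8.1).
- Effect of one affected subject with no other Grade 3+ AE on placebo: 1/62 = 0.016, or 1.6 percentage points on the placebo Grade 3+ rate.
- A subject who already has a Grade 3+ AE on placebo adds nothing to the overall Grade 3+ rate.
- The number of affected subjects cannot be derived from the documents.

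**4. Size for QT timing**
- ECGs are scheduled on Day 1 and Day 15 of Cycle 1 and on Day 1 of each later cycle (Protocol 10.5.4). With 28-day cycles, Cycle 2 Day 1 is 28 + 1 = Day 29 and Cycle 3 Day 1 is 2 × 28 + 1 = Day 57.
- The SAP 9.2 bands are up to 15, 16–30, 31–45, 46–60 and over 60 days.

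| Grade 1 first recorded | Grade 2 reached | Timed early by | Band if onset is used | Band if Grade 2 date is used |
|---|---|---|---|---|
| Day 15 | Day 29 | 29 − 15 = 14 days | up to 15 | 16–30 |
| Day 15 | Day 57 | 57 − 15 = 42 days | up to 15 | 46–60 |
| Day 29 | Day 57 | 57 − 29 = 28 days | 16–30 | 46–60 |
| Not recorded at Grade 1 | any | 0 | correct | correct |

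The bands are the same if time is counted as elapsed days (14, 28 and 56) instead of study days.

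**The case against.** A reader might infer that the SAP plans to tabulate AEs that worsen on AG-120 as placebo events. It does not. No onset-date allocation is written for AEs. SAP 7 defines the after-crossover period by data collected after crossover, SAP 9.1 counts worsening as well as onset, and SAP 10.3 resets the baseline. Read together, these point to counting the worsening in the after-crossover column. That part of the objection stands. It does not clear the placebo column, because the same event also began on placebo and its severity field may by then hold the later grade.

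A reader might also infer that the lost dates can never be recovered. The documents do not support this. The eCRF is not available, so it may capture grade changes. Section 11.2.4 does require the initial severity to be recorded. Grade 2+ QT events go to the sponsor as special-interest reports within 24 hours (Protocol 11.2.3.1), and ECG data are collected separately. However, SAP 9.2 does not say that these dates will be used, and SAP 9.7 categorises maximum QTcF without timing it. For symptomatic AEs the protocol and SAP name no comparable dated source.

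The affected group is limited. Serious worsening and recurrences already have their own dates. A Grade 1 QT change may never become an AE record, because Protocol 11.1.1 lists a deteriorating ECG as an AE when it comes with symptoms or leads to a treatment change.

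Finally, Protocol 11.5.1 follows AEs to resolution or stability, which might suggest that worsening long after the last dose inflates treatment-emergent grades. Protocol 8.5.1 and 11.2 limit follow-up to 28 days, and the SAP window matches them, so the point does not rest on this.

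**Conclusion.** The gap is real and should be closed. For non-serious AEs that continue across crossover and worsen on AG-120, following the recording rule can show the worst grade under placebo. For a QT AE first recorded at Grade 1, the Grade 2+ time can run from the Grade 1 onset, 14 to 42 days early in the examples shown.

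This rests on three assumptions: the onset date stays unchanged when severity is updated, the eCRF holds no grade-change date, and the analysis uses the AE record alone. Misallocation is then a risk that the plan leaves open, not a result that it prescribes. Any total percentage for the distortion would need a rate of crossover and a rate of worsening that the documents do not supply. Only the 1.6 points per affected subject can be derived. The efficacy analyses of PFS, OS and ORR are not touched.

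**What to change.** - **Protocol 11.2.4:** record each grade increase as a dated line, linked to the original event, that leaves the earlier grade in place.
- **SAP 9 and 9.1:** assign each grade to the period in which its date falls. The placebo column then uses the highest grade reached before crossover, and worsening after the first AG-120 dose counts in the after-crossover column.
- **SAP 9.2:** measure time to Grade 2+ QT prolongation to the first date on which Grade 2 is reached. For records already collected without a grade-change date, use the ECG date or the special-interest report date.

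The cost is one protocol sentence, an eCRF completion instruction, a few SAP sentences and one extra eCRF line per grade increase. Subjects are still counted once per preferred term. SAP Section 1 says the plan will be finalised before database lock, so the rules can still be pre-specified. If the eCRF already stores grade-change dates, only the SAP sentences are needed.

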11.2.5. Abnormal Laboratory Values

Not every laboratory abnormality qualifies as an AE. A laboratory test result should be reported as an AE if it meets any of the following criteria:

- a. Accompanied by clinical symptoms
- b. Results in a change in study treatment (eg, dosage modification, treatment interruption, or treatment discontinuation)
- c. Results in a medical intervention (eg, potassium supplementation for hypokalemia) or a change in concomitant therapy
- d. Clinically significant in the Investigator's judgment

It is the Investigator's responsibility to review all laboratory findings. Medical and scientific judgment should be exercised in deciding whether an isolated laboratory abnormality should be classified as an AE.

If a clinically significant laboratory abnormality is a sign of a disease or syndrome (eg, ALP and bilirubin $5 \times$ ULN associated with cholecystitis), only the diagnosis (ie, cholecystitis) should be recorded on the Adverse Event eCRF.

If a clinically significant laboratory abnormality is not a sign of a disease or syndrome, the abnormality itself should be recorded on the Adverse Event eCRF, along with a descriptor indicating if the test result is above or below the normal range.

11.2.6. Deaths

Deaths occurring during the protocol-specified AE reporting period (Section 11.2) that are attributed by the Investigator solely to progression of cholangiocarcinoma should be recorded only on the Treatment and Study Discontinuation eCRFs. All other on-treatment deaths, regardless of relationship to study treatment, must be recorded on the Adverse Event eCRF and reported to the Sponsor within 24 hours.

Death should be considered an outcome and not a distinct event. The underlying medical diagnosis or suspected diagnosis that caused or contributed to the fatal outcome should be recorded as the single medical concept on the Adverse Event eCRF. Generally, only 1 such event should be reported. The term “sudden death” should only be used for the occurrence of an abrupt and unexpected death due to presumed cardiac causes in a subject with or without preexisting heart disease, within 1 hour of the onset of acute symptoms or, in the case of an unwitnessed death, within 24 hours after the subject was last seen alive and stable. If the cause of death is unknown and cannot be ascertained at the time of reporting, “unexplained death” should be recorded on the Adverse Event eCRF. If the cause of death later becomes available (eg, after autopsy), “unexplained death” should be replaced by the established cause of death.

All deaths will be collected. All on-treatment deaths (within the 28 days after last dose of study treatment) should have an associated SAE captured for the event that led to death, except in the event of disease progression (see Section 11.2.7).

During post-treatment survival follow-up, all deaths will continue to be collected, but only those unrelated to disease progression will be classified as SAEs.

11.2.7. Progression of Cholangiocarcinoma

Progression of cholangiocarcinoma should not be reported as an AE if it is clearly consistent with the suspected progression of the underlying cancer as defined by RECIST v1.1 (Appendix 15.9). Clinical symptoms of progression may be reported as AEs if the symptoms cannot be determined as exclusively due to the progression of the subject’s underlying cholangiocarcinoma, or does not fit the expected pattern of progression for the disease.

If there is any uncertainty about an AE being due only to the disease under study, it should be reported as an AE or SAE.

11.2.8. Pre-existing Medical Conditions

A preexisting medical condition is one that is present at the Screening Visit for this study. Such conditions should be recorded on the Medical History eCRF.

A preexisting medical condition should be recorded as an AE only if the frequency, severity, or character of the condition worsens during the study. When recording such events on the Adverse Event eCRF, it is important to convey the concept that the preexisting condition has changed by including applicable descriptors (eg, “more frequent headaches”).

